8.6 Treatment Compliance

Patients will receive AdreView™ under direct supervision of study personnel. Information concerning the administration of AdreView™ (i.e., date, time, activity, and volume administered) will be checked and the code and volume per administration will be recorded in the patient's eCRF. Doses administered outside of specific dose requirements or defined range must be reported as protocol deviations (see Section 13.3).

9 STUDY PROCEDURES

All efficacy and safety measurements obtained during the course of the study are summarised in the Study Schedule of Events ([Table 1](#)).

Table 1 Study Schedule of Events

Variable	Screening / Enrolment Visit *	Randomisation	Post-Randomisation Procedures	Follow-Up Visit at 3 months post-ICD implantation (for patients with ICD implanted) (±15 days)	Follow-Up Visit at 6 months post-randomisation and then at least every 6 months (±15 days)	Second AdreView™ Administration at 2 years (±30 days) post-randomisation (low-risk cohort only)	End-of-Study Visit ^k
Informed consent ^a	X						
Inclusion/exclusion criteria	X						
Demographic Information	X						
Medical/Surgical History	X			X	X		X
Concomitant Medications ^b	X			X	X		X
Pregnancy Test ^c	X		X			X	
Pre-Inclusion Events	X						
Physical examination (complete)	X						
Brief Physical examination				X	X		X
Blood samples for clinical laboratory evaluation	X						
Vital signs ^d	X			X	X		X
ECG	X						
Check LVEF values within the previous 3 months or perform LVEF assessment. ^e	X						
Assignment to study group		X					
AdreView™ Administration ^f			X			X	
Injection site monitoring			X			X	
Image Acquisition (Planar and SPECT) ^{e, g}			X			X	
ICD Implantation (if applicable) ^h			X				
ICD interrogation (if applicable) ⁱ				X	X		X
AEs, SAEs and AdreView™-emergent AEs ^j	X	X	X	X	X	X	X
Data collection pertaining to primary and secondary endpoints			X	X	X	X	X

Table 1 Study Schedule of Events

Variable	Screening / Enrolment Visit *	Randomisation	Post-Randomisation Procedures	Follow-Up Visit at 3 months post-ICD implantation (for patients with ICD implanted) (± 15 days)	Follow-Up Visit at 6 months post-randomisation and then at least every 6 months (± 15 days)	Second AdreView™ Administration at 2 years (± 30 days) post-randomisation (low-risk cohort only)	End-of-Study Visit ^k
----------	-------------------------------	---------------	-------------------------------	--	--	---	---------------------------------

*All procedures listed do not necessarily need to be performed during a single day

- a Signed and dated informed consent must be obtained before eligibility assessments, including pregnancy test, are commenced.
- b Recorded up to 30 days before screening. Investigators should record all guideline-directed optimal medical therapy. Should any patients not be receiving guideline-directed optimal medical therapy at target dose per local guidelines, the investigator must document the reason(s) why in the source documents.
- c A serum or urine pregnancy test will be performed for all women of childbearing potential.
- d Before vital signs are measured, the patient should be resting for at least 5 minutes. The same arm and position will be used each time vital signs are measured for a given patient and blood pressure will be measured from the arm contra-lateral to the site of AdreView™ administration whenever possible.
- e Acceptable methods of LVEF assessment are radionuclide or contrast ventriculography, ECG-gated SPECT MPI, MR, CT, or 3D 2D echocardiography (Simpson's or multidisc method or equivalent only). Image files will be sent to the Sponsor.
- f AdreView™ will be administered to all patients. First AdreView™ administration should be performed in the 15 (+7) days post-randomisation. For the low-risk cohort only, a second AdreView™ administration should be administered at 2 years (± 30 days) post-randomisation, unless patient withdraws prior to study termination or has already received an ICD. In this case the second AdreView™ scan will be offered before withdrawal becomes effective. Thyroid blocking should be performed before administration of AdreView™ in accordance with the Package Insert/Summary of Product Characteristics/IB and local regulations unless the patient has had a complete thyroidectomy.
- g At 3 hours 50 minutes after administration of AdreView™, patients will undergo a 10-minute acquisition of planar images, and whenever possible followed by SPECT acquisition, according to the imaging manual. Patients with LVEF 25% to 35% with an H/M ratio ≥ 1.6 will have a second AdreView™ scan at 2 years (± 30 days) post-randomisation.
- h Patients in the randomised AdreView™ group who are assessed as high risk, and patients in the SoC group according to the standard of care in each investigational site derived from the local implementation of internationally accepted HF guidelines. ICD implantation should be performed according to clinical practice and should be performed within 45 days after randomisation.
- i ICD interrogation does not need to be performed on the same day as the corresponding follow-up visit. ICD interrogation may be done remotely within ± 5 days of the corresponding follow-up visit.
- j AdreView™-emergent AEs are defined as any AE which occurs within 24 hours after administration of AdreView™, and in addition any AE which occurs more than 24 hours after administration of AdreView™ for which a causal relationship is assumed by the investigator.
- k Patients will be enrolled and followed up until sufficient endpoints have accrued (247 primary endpoint events). All patients will then attend an end-of-study visit within 1 month.

9.1 Screening/Enrolment Visit

Signed and dated informed consent must be obtained from all patients prior to any screening procedures. All patients must satisfy all the inclusion criteria and none of the exclusion criteria listed in Sections 7.2 and 7.3.

It is not necessary for all procedures to be performed during a single day.

At the screening/enrolment visit, LVEF function determination will be performed in cases where a previous LVEF measurement is not available. If there is a previous LVEF measurement performed within 3 months of enrolment, the investigator will check that this measurement was performed when the patient had no hospitalisations for HF or acute coronary syndrome, or if such hospitalisation happened then the LVEF measurement was performed 40 days after the event. Acceptable methods for LVEF determination are as follows: radionuclide ventriculography, ECG-gated SPECT MPI, MR, CT, or 3D or 2D echocardiography (Simpson's or multidisc method or equivalent only, M-mode echocardiography is not accepted). LVEF images will be sent to the sponsor in electronic format.

The following parameters will be collected:

- Demographics
- Medical history
- Concomitant medications, including guideline-directed optimal medical therapy. Should any patients not be receiving guideline-directed optimal medical therapy at target dose per local guidelines, the investigator must document the reason(s) why in the source documents.
- Vital signs (blood pressure, heart rate, respiratory rate, and pulse oximetry)
- Blood samples for serum chemistry and haematology and BNP or N-terminal pro b-type natriuretic peptide (NT proBNP) determination will be collected (according to [Table 2](#))
- Physical examination will be performed
- All female patients will undergo a serum or urine pregnancy test unless surgically sterile or post-menopausal
- A 12-lead ECG will be performed
- Collection of pre-inclusion events will commence

Waivers or protocol exceptions will not be granted prospectively by the Sponsor under any circumstances. Any exceptions to protocol-specified requirements will be considered as protocol deviations.

9.2 Randomisation

Randomisation to the AdreView™ or SoC groups will be done remotely through an electronic data capture system. Once the investigator has reviewed and properly entered the requested data, the electronic system will allocate the patient to the appropriate cohort should the patient be allowed to pursue the study. The primary randomisation is to one of 2 treatment methods in a 1:1 ratio stratified by enrolling centre.

Patients with $25\% \leq \text{LVEF} \leq 35\%$ will be randomly assigned to the AdreView™ group or the SoC group via an IWRS. They will be scheduled for an AdreView™ scan to be performed within 15 (+7) days post-randomisation.

The following procedures will be performed and parameters will be collected:

- Assignment to study group
- Collection of AEs and SAEs will commence, as well as study endpoints.

9.3 Post-Randomisation Procedures

All female patients (unless pre-menarchal, surgically sterile or post-menopausal) will undergo a serum or urine pregnancy test on the day of and prior to AdreView™ administration. AdreView™ dosing will only commence if the result is negative.

AdreView™ will be administered to all patients.

The first AdreView™ administration should be performed in the 15 (+7) days post-randomisation. Starting at 3 hours 50 minutes after administration of AdreView™, patients will undergo a 10-minute acquisition of anterior planar images of the thorax, and whenever possible these will be followed by a SPECT acquisition. Details of the acquisition and transmission of images to the Sponsor are provided in the study Imaging Manual.

Only those patients allocated to the AdreView™ arm will have the results of the scan (H/M ratio calculated on an anterior planar image obtained at 3 hours and 50 minutes for 10 minutes, and with regions placed following the standard quantification method according to the Imaging Manual) available to make a decision on the need for implantation of an ICD. In patients allocated to the SoC group, the investigator will remain blinded to the results of the AdreView™ images and any information derived from them in order not to influence the decision to implant or not implant an ICD.

Patients in the AdreView™ arm who are deemed at high-risk for all-cause and cardiovascular mortality (H/M ratio <1.6 as defined in Section 6.1) will undergo ICD device implantation. ICD implantation should be performed within 45 days of randomisation. Patients deemed to be at low risk (H/M ratio ≥ 1.6 as per Section 6.1) will continue to receive guideline-directed optimal medical therapy but will not undergo ICD implantation. In the low risk group, a second AdreView™ scan will be performed at 2 years following the first scan, or in case of early withdrawal, prior to this withdrawal being effective.

Patients randomly allocated to the SoC group will undergo ICD implantation and will be managed and followed up in accordance with internationally accepted HF guidelines. ICD implantation should be performed within 45 days of allocation to the SoC group. The results of the AdreView™ scan will remain blinded to the investigator to avoid any influence regarding patient management. AEs, SAEs and AdreView™-emergent AEs will be recorded.

All data related to primary and secondary endpoints will be collected.

Injection site monitoring will be performed before and after injection (with findings recorded pre-administration, 15 minutes post-administration, and at discharge from the imaging suite).

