8.4 Blinding and Measures to Minimise Bias

Neither patients nor site personnel (including the on-site AdreView™ scan reviewer) can be blinded to group assignment. Sites must know whether patients are randomised to the AdreView™ or SoC groups in order to use the results of the scans in the AdreView™ group. For patients in the randomised SoC group the investigator will remain blinded to the results of the AdreView™ scan.

Both the DSMB and the CEAC will review patient data while blinded to enrolment group. The DSMB could, should it be regarded as necessary for their analysis, also review patient data in an unblinded fashion.

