8.5 Prior and Concurrent Therapy

Any medications taken by the patient within 30 days before and up to the end of study visit will be recorded in the eCRF along with the indication and dosage, including but not restricted to guideline-directed optimal medical therapy. Either the generic or the trade name may be recorded. The Sponsor/CRO will encode all therapy and medication according to a current well-recognised dictionary of medical codes.

Should any patients not be receiving guideline-directed optimal medical therapy at target dose per local guidelines, the investigator must document the reason(s) why in the source documents.

As stated in the exclusion criteria, patients will not be allowed to take any medications known or suspected to interfere with AdreView™ imaging as per Package Insert (or Summary of Product Characteristics or IB as applicable) for at least 5 half-lives prior to administration of AdreView™. The investigator will be responsible for assessing the patient's medication in order to determine whether the medication should be withdrawn for the required period. In the case of a patient requiring medications that can interfere with AdreView™ imaging and where the clinical status does not allow temporary withdrawal of the medication, the investigator may elect to withdraw the patient from the study on safety grounds.

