10.1.5 Image Interpretation and Correlation with Standard of Truth

AdreView™ images will be analysed according to standard procedures as laid out in the Imaging Manual. Planar images will be analysed as per the FDA-approved label (i.e., USA version Package Insert) where regions of interest (ROIs) will be placed in mediastinum and whole heart to calculate H/M ratio by nuclear medicine department personnel. These Imaging Manual instructions (based on the USA version of the Package Insert) agree with procedures and/or guidances approved by the Health Authorities for all countries in which the product is approved for scintigraphy assessment of sympathetic innervation of the myocardium. If sites from any additional countries are added to the study, they must follow the instructions in the Imaging Manual for acquisition of images and calculation of H/M, regardless of any potential differences with local guidances that may exist. The GE-122-020 Imaging Manual will describe image acquisition (planar and SPECT), processing (planar only) and analysis (planar only). AdreView™ planar image analysis and quantification will be performed on-site and there will be no central blinded reads. Results of the H/M ratio will be correlated with the patient's clinical outcome.

All AdreView™ planar and SPECT images will be sent to the Sponsor's central laboratory for further analysis. SPECT images will be analysed in a blinded manner. Results of the quantification of the regional distribution will be compared with clinical parameters (i.e., ECG, NYHA, LVEF, etc.) and efficacy endpoints, to assess for any trends in order to generate working hypothesis for future studies. Analysis of SPECT images collected during the study will be done in an exploratory manner and may be reported separately.

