12.6.1 Efficacy Endpoints and Analyses (Secondary)

Key Secondary Endpoints

- A composite of the proportion of patients with hospitalisation or death related to major complications of device implantation (i.e., need for thoracotomy, pericardiocentesis, or vascular surgery) or complications of long-term device therapy (i.e., infection not leading to hospitalisation, lead and/or generator removal/replacement, inappropriate shocks, explantation). This endpoint will be analysed for superiority. These proportions will be compared between the patients with $H/M \geq 1.60$ in the AdreView™ group and the patients with $H/M \geq 1.60$ in the SoC group, using the Cochran-Mantel-Haenszel test stratified by enrolling centre, using a 2-sided alpha value of 0.050.

- Cardiac death. The occurrence of this event will be analysed in the primary efficacy population using a Cox proportional hazards model as was performed in the primary efficacy analysis (non-inferiority [NI], using an NI margin of 1.20).
- Rate of hospitalisation for cardiovascular cause. This rate will be compared between the AdreView™ and SoC groups using the Miettinen and Nurminen methodology [\[Miettinen and Nurminen 1985\]](#), (non-inferiority [NI], using an NI margin of 1.20).
- Rate of all-cause hospitalisation. This rate will be compared between the AdreView™ and SoC groups using the Miettinen and Nurminen methodology [\[Miettinen and Nurminen 1985\]](#), (NI, using an NI margin of 1.20).
- A composite of the occurrence of resuscitated life-threatening ventricular tachycardia, unstable ventricular tachy-arrhythmias, SCD and resuscitated cardiac arrest. The occurrence of this event will be analysed in the primary efficacy population using a Cox proportional hazards model as was performed in the primary efficacy analysis (non-inferiority, using an NI margin of 1.20).

Additional Secondary Endpoints

- Syncope. The occurrence of this event will be analysed in the primary efficacy population using a Cox proportional hazards model as was performed in the primary efficacy analysis (non-inferiority, using an NI margin of 1.20).

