Patients with $25\% \leq \text{LVEF} \leq 35\%$, and meeting all other inclusion criteria and not meeting any of the exclusion criteria, were enrolled and randomly assigned to the AdreView™ group or the SoC group in a ratio of 1:1. All patients were to be scheduled for an AdreView™ scan. The results of the AdreView™ scan in the SoC group were to remain blinded to the investigator to avoid any influence in the decision of implanting an ICD. The binary assessment of risk (i.e., either high or low) was made for the AdreView™ patient group based on the H/M measurement made by the site personnel on the AdreView™ planar image (i.e. H/M < 1.6 was high risk vs H/M ≥ 1.6 was low risk). Only the high/low risk classification was made known to the investigator and as such was used to determine ICD implantation in the AdreView group per protocol. Patients with AdreView™ H/M ratio < 1.6 (high 1- and 2-year mortality risk) were to undergo ICD device implantation. Patients with AdreView™ H/M ratio ≥ 1.6 (low 1- and 2-year mortality risk) continued to receive guideline-directed optimal medical therapy according to clinical standard practice and did not undergo ICD implantation initially, but could receive an ICD at a later stage should they develop further symptoms and after assessment by the investigator. Patients in this latter group were to undergo a second AdreView™ scan (planar and possibly SPECT) 2 years post-randomisation for purposes of re-stratification. Patients allocated to the SoC group were to undergo ICD implantation and to be managed and followed up in accordance with internationally accepted HF guidelines.

Patients were to attend follow-up visits at the rate determined by the investigator, in accordance with their clinical standard practice. However, a follow-up visit had to take place at least every 6 months (an extra follow-up visit was to be performed at 3 months after ICD implantation). All patients were also to attend an end-of-study visit.

Table 1 Study Schedule of Events

Variable	Screening / Enrolment Visit *	Randomisation	Post-Randomisation Procedures	Follow-Up Visit at 3 months post-ICD implantation (for patients with ICD implanted) (± 15 days)	Follow-Up Visit at 6 months post-randomisation and then at least every 6 months (± 15 days)	Second AdreView™ Administration at 2 years (± 30 days) post-randomisation (low-risk cohort only)	End-of-Study Visit ^k
Informed consent ^a	X						
Inclusion/exclusion criteria	X						

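### Randomisation does not protect the H/M ≥ 1.6 comparison in the first key secondary endpoint, because H/M is measured after allocation, on site, by readers who know the arm

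*Protocol*

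**What the plan says.** Randomisation is stratified by enrolling centre only (Protocol 6.2, 9.2). The scan follows: "The first AdreView™ administration should be performed in the 15 (+7) days post-randomisation" (Protocol 9.3), so it may fall as late as day 22. For the SoC arm the same section says "ICD implantation should be performed within 45 days of allocation to the SoC group". It gives no earliest day and does not make the implant wait for the scan. Table 1 lists scan and implantation in one post-randomisation column.

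On reading, Protocol 8.4 states "Neither patients nor site personnel (including the on-site AdreView™ scan reviewer) can be blinded to group assignment", and Protocol 10.1.5 states "AdreView™ planar image analysis and quantification will be performed on-site and there will be no central blinded reads". SAP 2.2 confirms that the risk class is "based on the H/M measurement made by the site personnel on the AdreView™ planar image".

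The analysis of the first key secondary endpoint (Protocol 12.6.1) reads "These proportions will be compared between the patients with" H/M ≥ 1.60 in each arm, by a Cochran-Mantel-Haenszel test; SAP 5.4.3.1 keeps the comparison but stratifies by country. Under Protocol 12.6 this endpoint gates all later key secondary tests. Missing values stay missing (Protocol 12.11; SAP 5), and neither document says what to do with a randomised patient who has no H/M.

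**The concern.** A subgroup defined by a baseline trait keeps the protection of randomisation if the trait is obtained for everyone and measured identically in both arms. The plan does not secure either condition, for three reasons.

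1. **Scan order.** In the AdreView arm the initial implant decision waits for H/M. In SoC it does not. An SoC patient who is implanted first, and who then dies or is too ill ever to be scanned, has no H/M and leaves the comparison. The harm that the endpoint exists to count goes with that patient. The initial implant in the AdreView arm has no equivalent loss.
2. **Missing H/M.** Any arm difference in scan completion changes who is compared. Protocol 8.5 adds one way for a scan not to happen: where an interfering drug cannot be stopped, "the investigator may elect to withdraw the patient from the study on safety grounds", and by then the arm is known.
3. **Reading.** Only in the AdreView arm does a value just above or below 1.6 decide whether a device is given, and the reader knows which arm it is.

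At stake are the size of the device-harm benefit in low-risk patients and, under the Protocol's hierarchy, the gate to the remaining key secondary tests.

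**Working it through.** **Plan's own figure.** Protocol 12.10 gives 156 to 486 patients in total with H/M ≥ 1.6, using two-sided alpha 0.05, power of 80% or 90%, SoC harm of 5% to 10%, and AdreView harm of 0.0001.
- Upper end (5%, 90% power, normal approximation with continuity correction): 243 per arm, total 486. Reproduced.
- Lower end (10%, 80% power): Fisher's exact test gives power 0.792 at 77 per arm and 0.802 at 78, so the total is 156. Reproduced, but by a different method; the continuity-corrected formula gives 186. This does not affect the point.

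**Size of the subgroup.** Using the LVEF split of 1:4 and the H/M shares in Protocol 12.8: 0.2 × 21% + 0.8 × 25% = 24.2%. Then 0.242 × 2001 = 484, or about 240 per arm. The plan says approximately 500.

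**Windows.** The latest planned scan day is 15 + 7 = 22. The implant window closes at day 45, which leaves 45 − 22 = 23 days. An SoC implant can precede the scan, and a scan-first order would fit both windows.

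**Power at 240 per arm** (normal approximation, no continuity correction, no stratification):

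z = (|p1 − p2| − 1.96 × √[p̄(1 − p̄)(1/n1 + 1/n2)]) / √[p1(1 − p1)/n1 + p2(1 − p2)/n2]

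With p1 = 0.05 and p2 = 0.0001: (0.0499 − 1.96 × 0.01427) / 0.01408 = 1.56, so power is 94.0%.

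**Lost SoC events.** At 5%, 0.05 × 240 = 12 SoC patients have an event. If a fraction f of them never get an H/M, they leave both numerator and denominator. The values of f are assumptions; the documents give none.
- f = 10%: 10.8/238.8 = 4.5% observed
- f = 25%: 9/237 = 3.8% observed
- f = 50%: 6/234 = 2.6% observed

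| True SoC rate | Power, f = 0 | f = 10% | f = 25% | f = 50% |
|---|---|---|---|---|
| 5% | 94.0% | 91.5% | 86.0% | 69.8% |
| 7% | 98.8% | 97.8% | 95.2% | 84.0% |
| 10% | 99.9% | 99.8% | 99.2% | 94.6% |

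**Would an arm difference in reading be visible?** Take about 1000 patients per arm and low-risk shares of 28% against 24%. Then z = 0.04 / √(0.28 × 0.72/1000 + 0.24 × 0.76/1000) = 0.04/0.0196 = 2.04. Comparing the shares would reveal only a fairly large shift.

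**The case against.** The strongest reply is that H/M is meant to be a patient characteristic. It is measured in every patient by one Imaging Manual method, and in the AdreView arm it precedes the initial implant decision. Measuring it within 22 days of allocation does not in itself make the groups differ. That stands: the documents show that comparability is unprotected, not that it is lost.

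Three stronger readings are tempting and should not be drawn.
- **Every SoC harm before the scan is lost.** No passage excludes a late scan, and SAP 5 applies no visit windows, so loss requires that the scan never happens. Much of the endpoint is also long-term (infection, lead or generator replacement, inappropriate shocks, explantation), which a missed early scan exposes far less. That SoC implants come first is itself an inference from the windows and the absence of a sequence rule.
- **Arm-aware reading could reshape a fifth of the group.** This needs 5% of all readings to cross 1.6 in one direction: 50/240 = 21%. Only readings near 1.6 are exposed. If 20% of 1000 lie there, 5% of 200 is 10 patients, or 4% of 240. Both shares are assumptions; the documents give no reader variability and no direction.
- **SoC scans are more likely to be skipped, or withdrawals to differ by arm.** The scan is required for everyone, Protocol 9.1 rules out waivers, and the 8.5 option applies to both arms.

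There are partial safeguards. Nuclear medicine staff calculate H/M (Protocol 10.1.5). Investigators do not see SoC results (Protocol 8.4), and under the SAP they see only the risk class (2.2) and not the H/M value (2.5). None of these blinds the reader to arm. The same composite is also planned in all randomised patients (Protocol 12.6.1; SAP 5.4.3.2). That version keeps every SoC implant harm but does not answer the question in low-risk patients.

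**Conclusion.** The point holds in a limited form. The two H/M ≥ 1.6 groups are not protected by randomisation, because the defining measurement follows allocation, is read with the arm known, may follow an SoC implant, and has no rule for missing values. The actual bias cannot be computed: the documents give no missing-scan rate, no share implanted before the scan, and no reader variability.

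On the assumed range, and if only SoC events are lost, the cost is modest unless the loss is large or the SoC rate is at the bottom of the planned range. Such loss understates AdreView's advantage and cannot create a false claim for it. The effect of arm-aware reading has no known direction. The planned contrast, about 0% against 5% to 10%, arises mainly from not implanting, so its direction is probably robust provided later implants in the low-risk group are few.

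The scan-order, missing-H/M and reading routes do not affect the primary analysis. After the sponsor's early termination, SAP 5.4.4 drops the hierarchy and treats all secondary endpoints as reference only, which further limits the consequence.

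**What to change.** **Protocol 9.3.** Require that the first scan is done and H/M locked before any ICD implantation in either arm. This fits the existing 22-day and 45-day windows, so neither needs to change. The cost is that some SoC implants would be scheduled later within their window. In a terminated study this helps only patients not yet implanted, or a successor trial.

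**SAP**, which is still usable because it is to be signed before database lock:
- Report by arm the unscanned patients, the order of scan and implant, the share with H/M ≥ 1.6, and device events, including those in unscanned patients.
- Add a sensitivity analysis that keeps unscanned patients in their randomised arm and counts their device events.
- Present the result beside the all-randomised composite already planned.

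These cost a few tables and one extra analysis. Optionally, add a planar re-read blinded to arm, as a sensitivity analysis only. All planar images already go to the sponsor's central laboratory, so the cost is reader time.

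**Similar future trial.** Scanning before allocation and stratifying by H/M class would give direct protection, provided those who decide on randomisation cannot see H/M. Without that condition it exchanges one selection problem for another. It needs no extra scan per randomised patient, but screening lengthens by up to about three weeks and a few patients are scanned and never randomised.
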